8.1 Definitions and reports of adverse events

All adverse events that occur after the informed consent is signed (including run-in) must be recorded on the adverse event CRF (paper and/or electronic) whether or not related to study agent. AE Data Elements including:

- AE reported date
- AE Verbatim Term
- CTCAE Term (v 5.0)
- Event onset date and event ended date
- Severity grade
- Attribution to study agent (relatedness)
- Whether or not the event was reported as a Serious Adverse Event (SAE)
- Action taken with the study agent
- Outcome of the event
- Comments

Identify the adverse event using the NCI Common Terminology Criteria for Adverse Events (CTCAE) version 5.0. The CTCAE provides descriptive terminology and a grading scale for each adverse event listed.

Study: TASP-UTUC

Version: 1

Date: 17/10/2024

NTUH Clinical Trial Protocol

AEs will be assessed according to the CTCAE grade associated with the AE term. AEs that do not have a corresponding CTCAE term will be assessed according to their impact on the participant's ability to perform daily activities.

The possibility that the adverse event is related to study drug will be classified as one of the following: not related, unlikely, possible, probable, definite.

8.2 Serious Adverse Events

ICH Guideline E2A and GCP of Taiwan define serious adverse events as those events, occurring at any dose, which meet any of the following criteria:

- Results in death
- Is life threatening (Note: the term life-threatening refers to an event in which the patient was at risk of death at the time of the event; it does not refer to an event which hypothetically might have caused death if it were more severe).
- Requires inpatient hospitalization (outside of planned combined treatment pathway) or prolongation of existing hospitalization
- Results in persistent or significant disability/incapacity
- Is a congenital abnormality/birth defect
- Events that may not meet these criteria, but which the investigator finds very unusual and/or potentially serious, will also be reported in the same manner.

8.3 Adverse event follow-up

All AEs, including lab abnormalities that in the opinion of the investigator are clinically significant, will be followed according to good medical practices and documented as such. Site staff should send follow-up reports as requested when additional information is available. Additional information should be entered on the IRB of NTUH of SAE form in the appropriate format. Follow-up information should be sent to NTUH IRB as soon as possible according to IRB's Serious Adverse Event Reporting Procedures and Guidelines.

9. Statistical Considerations

9.1 Sample size determination

This trial is not designed for registration purpose, so that there is no formal testing or statistical calculation. This trial evaluates initial feasibility, not for efficacy or larger scale safety study. Therefore, this trial will not expose too many patients to pre-market SP Surgical System. Sample size is based on several factors: surgeon's experience of multi-port, pre-study training, and pre-clinical cadaver study of SP system. It is estimated that 20 patients is sufficient (passing learning curve or representative dataset) for this small feasibility study.

9.2 Planned statistical methods of analysis

Quantitative variables will be presented as mean±standard deviation (SD) and categorical variables will be presented as proportions. The Student t-test, Mann-Whitney U-test and Spearman rank correlation test will be used to analyze differences between groups of variables.

Study: TASP-UTUC

Version: 1

Date: 17/10/2024

NTUH Clinical Trial Protocol

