	
8. Severe concomitant illness that drastically shortens life expectancy or increases risk of therapeutic interventions, such as: severe heart disease (NYHA functional class III-IV) or severe lung disease (GOLD Group C-D)9. Cannot follow trial-required procedures10. Concomitant systemic or pelvic disease that increases the risk of surgery11. Long-term use of anti-coagulant(s)12. Patients with coagulopathy13. Emergency surgery
Design of trial:	
• Prospective• Interventional• Open label• Single arm• Study period: 2 years (From Dec/1/2024 to Nov/30/2026)• Study site: single center study
Study treatment:	Radical nephroureterectomy and ipsilateral bladder cuff resection using da Vinci SP Surgical System (robotic surgery)
Primary endpoint:	Success without conversion to alternative surgery
Statistical analysis and sample size estimation:	
• Statistical methods: Descriptive methods will be used.• Interim analysis: No• Efficacy assessment group: Per Protocol• Estimated sample size:
○ Enroll: 25○ Evaluable: 20

Table of Content

Clinical Trial Protocol.....	1
Synopsis	2
Table of Content.....	4
Abbreviations.....	6
1. Introduction	7
1.1 Background and rationale	7
1.1.1 Medical background	7
1.1.2 Animal and preclinical study	8
1.2 Investigational product	8
1.3 Risks and benefits assessment	9
1.4 Regulatory	10
2. Objectives and Endpoints.....	10
2.1 Study objectives	10
2.1.1 Primary objective	10
2.1.2 Secondary objectives.....	10
2.1.3 Other exploratory objectives (if any).....	10
2.2 Study endpoints.....	10
2.2.1 Primary endpoint.....	10
2.2.2 Secondary endpoints	10
2.2.3 Other exploratory endpoints (if any).....	10
3. Study Design.....	11
3.1 Overall design.....	11
3.1.1 Recruitment plan.....	11
3.2 Study calendar.....	12
3.3 Criteria of Termination of the Trial.....	13
4. Study Population	13
4.1 Inclusion criteria	13
4.2 Exclusion criteria.....	13
4.3 Withdrawal criteria.....	13
5. Treatment	14

Study: TASP-UTUC

Version: 1

Date: 17/10/2024

NTUH Clinical Trial Protocol

5.1	Treatment administration	14
5.2	Concomitant therapy	14
6.	Efficacy Assessments	14
7.	Safety Assessments.....	15
8.	Adverse Event Reporting.....	15
8.1	Definitions and reports of adverse events.....	15
8.2	Serious Adverse Events.....	16
8.3	Adverse event follow-up	16
9.	Statistical Considerations.....	16
9.1	Sample size determination.....	16

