3.1.1 Recruitment plan

This trial plans to recruit 20 evaluable patients at single trial site, NTUH. Assuming screening failure and drop-out of 5 patients, at least 25 patients will be screened (enrolled). Recruitment is estimated to complete within 1 year with recruitment rate of 0.5 patient per week.

Study: TASP-UTUC

Version: 1

Date: 17/10/2024

NTUH Clinical Trial Protocol

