5.2 Concomitant therapy

Medical treatment of underlying chronic diseases (such as diabetes or hypertension) is allowed.

6. Efficacy Assessments

- Primary endpoint: Success without conversion to alternative surgery: successful completion of radical nephroureterectomy and bladder cuff resection with da Vinci SP system (no conversion to conventional laparoscopic, multiport da Vinci surgery or open surgery; addition of access port to complete the procedure would not be considered as conversion.)
- Operative time (min): first skin incision to closure of wound
- Console time (min): the time when the surgeon starts the console work till the specimen is taken out from the patient
- Estimated blood loss (mL): measured at operating suite
- Length of hospital stay (day): the duration from operation day to the discharge day (included)
- Pain score: measured by Visual Analogue Scale (VAS)

Other assessments:

- Patient demographics and medical history
- Pathology assessment
- Body mass index, body weight
- Analgesic use/types: opioid or non-opioid, changes in post-operative period)

Study: TASP-UTUC

Version: 1

Date: 17/10/2024

NTUH Clinical Trial Protocol

7. Safety Assessments

- Safety labs (complete blood count and other routine tests)
- Estimated blood loss (mL): measured at operating suite.
- Transfusion: record of blood product received.
- Complication (intraoperative and/or postoperative) (Clavien Dindo grading)
- Readmission (in 30 days)
- Reoperation (in 30 days)
- Perioperative mortality (in 30 days)

8. Adverse Event Reporting

Upon the occurrence of serious adverse events (SAE) which result in serious malfunctioning of the medical device, [name] [name] will report SAEs to the IRB of NTUH according to the Serious Adverse Event Reporting Procedures and Guidelines posted by NTUH. SAE reports to the IRB should include the following information when calling the Medical Monitor:

- Date and time of the SAE
- Date and time of the SAE report
- Name of reporter
- Call back phone number
- Affiliation/Institution conducting the study
- Protocol number
- Title of protocol
- Description of the SAE, including attribution to drug and expectedness

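### Section 9.2 names mean±SD as the summary for every quantitative outcome and no median, IQR or range, which in about 20 patients can describe blood loss and length of stay poorly (minor)

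*Protocol*

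**What the plan says.** Section 9.2 of the protocol sets one presentation rule: "Quantitative variables will be presented as mean±standard deviation (SD) and categorical variables will be presented as proportions". No quantitative variable is exempted, and no other section names a median, an IQR, a range or a transformation. The next sentence of section 9.2 names a t-test and two rank-based methods: "The Student t-test, Mann-Whitney U-test and Spearman rank correlation test will be used to analyze differences between groups of variables".

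Five secondary endpoints fall under the rule: operative time, console time, blood loss, length of stay and pain score (sections 2.2.2 and 6). Section 6 defines two of them as "Estimated blood loss (mL): measured at operating suite" and "Length of hospital stay (day): the duration from operation day to the discharge day (included". Pain is a VAS score whose range is not given.

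The synopsis describes the approach as "Statistical methods: Descriptive methods will be used", and section 9.1 says that nothing is formally tested. On size, section 3.1.1 says "This trial plans to recruit 20 evaluable patients at single trial site, NTUH".

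On who is analysed, section 9.2.3 takes every operated patient, while the synopsis gives Per Protocol as the efficacy group.

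**The concern.** In a single-arm descriptive study, the summary statistics are the secondary results. Mean and SD give a fair picture of the typical patient when values are spread roughly evenly around a centre. Two of the five outcomes are unlikely to behave that way. Blood loss cannot fall below 0 mL. Length of stay, counted with the discharge day included, cannot fall below 1 day. Both can run far upward in a patient with a complication.

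The protocol allows for such patients. Section 1.3 lists bleeding and adjacent organ injury among the risks. The numerical stopping rule in section 3.3 is reached only at 2 deaths or 5 severe morbidities, so a completed series could contain up to 4 severe morbidities.

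At stake is whether a reader of the results can tell what an ordinary single-port case looked like, or sees a figure shaped largely by one patient.

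**Working it through.** **The plan's own figure.** 20 evaluable + 5 screening failures and drop-outs = 25 enrolled, as section 3.1.1 states. The 20 has no statistical derivation to reproduce, and the protocol gives no SD or expected value for any outcome. The check therefore uses n = 20 with general algebra and assumed data.

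**General result.** Take 19 patients with mean m and SD s, and one further patient at m + k·s.
- Shift in the mean = k/20, in units of s.
- SD ratio (20 patients against 19) = √[(18 + 0.95k²)/19].
- Share of the total sum of squares due to that patient = 0.95k²/(18 + 0.95k²).

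| k | Mean shift (in s) | SD ratio | Share of sum of squares |
|---|---|---|---|
| 3 | 0.15 | 1.18 | 32% |
| 5 | 0.25 | 1.48 | 57% |
| 10 | 0.50 | 2.44 | 84% |
| 20 | 1.00 | 4.58 | 95% |

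The SD is affected more than the mean.

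**Assumed data, 19 patients plus one.** The 19 base values are:
- Blood loss (mL): 50 (×5), 100 (×7), 150 (×4), 200 (×3).
- Stay (days): 3 (×4), 4 (×7), 5 (×5), 6 (×3).
- Operative time (min): 180, 190, 200, 200, 210, 210, 220, 220, 230, 230, 240, 240, 250, 250, 260, 270, 280, 290, 300.
- VAS (0-10 assumed): 0, 1 (×3), 2 (×5), 3 (×5), 4 (×3), 5 (×2).

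| Outcome | Added case | Mean±SD, 19 → 20 patients | Median, 19 → 20 (IQR of 20) |
|---|---|---|---|
| Blood loss, mL | 500 | 113±52 → 133±100 | 100 → 100 (88-150) |
| Blood loss, mL | 1,000 | 113±52 → 158±205 | 100 → 100 (88-150) |
| Stay, days | 10 | 4.4±1.0 → 4.7±1.6 | 4 → 4 (4-5) |
| Stay, days | 20 | 4.4±1.0 → 5.2±3.6 | 4 → 4 (4-5) |
| Operative time, min | 360 | 235±34 → 242±43 | 230 → 235 (210-263) |
| Operative time, min | 600 | 235±34 → 254±88 | 230 → 235 (210-263) |
| VAS | 10 | 2.6±1.4 → 3.0±2.1 | 3 → 3 (2-4) |

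Check for the 1,000 mL case: k = (1,000 − 113.2)/52.3 = 17.0. The SD ratio is √[(18 + 0.95 × 17.0²)/19] = 3.9, and 52.3 × 3.9 ≈ 205.

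**Bound for VAS.** On a 0-10 scale, one patient in 20 can move the mean by at most 10/20 = 0.5 point.

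**How likely is such a case?** The chance of at least one in 20 is 1 − (1 − p)²⁰: 33% at an assumed rate of 2%, 64% at 5% and 88% at 10%.

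**Does the case enter the summary?** A complicated but unconverted patient does so under all operated patients and, on any ordinary reading, under Per Protocol. Section 4.3 withdraws patients for morbidity only when it is unrelated to the surgery. For a converted patient, the two population statements give no settled answer.

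**The case against.** The strongest reply is that section 9.2 contains no error. Mean and SD are valid descriptions of any distribution with finite variance, and no interval or test is built on them here. Several stronger readings are tempting, but the documents do not support them.

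- *Only mean±SD will be reported.* The text does not exclude other summaries, and an SAP that is not at hand could add them. What stands is that the protocol names one summary for all quantitative variables and no other.
- *The plan assumes symmetry, and a mean minus SD below zero shows it is wrong.* The protocol states no such assumption and does not use mean±SD as a range of values. Naming rank-based methods in the same section does not establish one either.
- *One case dominates every outcome.* It does not. The effect is modest for a 10-day stay or a 360-minute operation and is capped for VAS. It is large only for extreme values of blood loss or stay.
- *Converted patients are averaged in unseen.* This cannot be stated as fact while all operated patients (section 9.2.3) and Per Protocol (synopsis) stand unreconciled.
- *The results would be poor inputs for a later study.* Mean and SD are the usual inputs for sample-size formulas, which is a reason to keep them.

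It is also fair that the skewness and the data sets above are assumed. Eligibility (ASA 1-2, BMI limits, no coagulopathy, no emergency surgery) narrows the population, though it does not remove complications. Finally, the individual values are collected in any case, so medians could be added at reporting.

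**Conclusion.** The point holds as a minor one. A single summary is named for all quantitative variables, and for blood loss and length of stay it is likely to be a weak description in a series of this size. With one extreme case in 20, the illustrated SD rises about 3.9-fold for blood loss (1,000 mL) and about 3.6-fold for stay (20 days). The mean rises by 44 mL and 0.8 day, and the medians do not move. The effect is smaller for operative time and, by analogy, console time, and minor for VAS.

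This rests on three assumptions: right skew in blood loss and stay, the illustrative values, and a 0-10 VAS. The primary endpoint, a proportion, is unaffected, and no threshold or stopping rule depends on this choice. The reason to act is that a better description costs almost nothing.

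**What to change.** In section 9.2, state that operative time, console time, blood loss, length of stay and VAS pain are presented as median, IQR and range in addition to mean±SD. If an SAP already provides this, align the protocol sentence with it.

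Separately, reconcile the analysis population in the synopsis with section 9.2.3. If converted patients are then included in these summaries, also list their values individually beside the summary.

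The cost is one sentence in section 9.2 and, if needed, a short listing. No new data, visits or patients are required.

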9.2.1 Efficacy analysis

Success rate for the completion of radical nephroureterectomy and bladder cuff resection with da Vinci SP System without conversion will be presented as proportions.

9.2.2 Safety analysis

All operated patients will be included in safety analysis. Related AE and complications will be described.

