1.3 Risks and benefits assessment

Risks:

1. Perioperative risks related to the surgeries: bleeding, wound infection, adjacent organ injury, wound dehiscence

2. Fail to perform the surgery successfully with SP system: conversion to multiport robotic or traditional endoscopic surgery or open surgery

Potential Benefits:

1. Cosmetic benefit: single incision or fewer scars at belly

Study: TASP-UTUC

Version: 1

Date: 17/10/2024

NTUH Clinical Trial Protocol

2. Peri-operative benefits: shorter hospital stays, less complication, less pain and less analgesic use, less CO₂ retention and oxidative stress related to pneumoperitoneum, improvement of disease symptoms and quality of life.

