4.3 Withdrawal criteria

1. Patients refuse to continue follow up per protocol during the study period
2. Patients developing mortality or morbidity during or within 30 days after the surgery that do not have consequential correlations with the surgical procedures (such as those resulting from natural disaster, war, or unexpected accidents)

5. Treatment

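### Section 8 triggers the IRB report only for SAEs that cause device malfunction, which is narrower than 8.2; secondarily, 9.2.2 commits only to related AEs, judged against a drug the trial does not have

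*Protocol*

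**What the plan says.** **SAE reporting.** Section 8 opens with the condition for reporting to the IRB: "Upon the occurrence of serious adverse events (SAE) which result in serious malfunctioning of the medical device". Reports then follow the hospital's posted SAE procedures. Section 8.2 defines an SAE by death, threat to life, unplanned or prolonged hospitalisation, lasting disability or birth defect. It adds that events outside these criteria which the investigator finds very unusual or potentially serious are reported in the same way. Section 8.3 sends SAE follow-up information to the IRB. Neither 8.2 nor 8.3 mentions malfunction.

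**AE recording and analysis.** Under Section 8.1 all AEs after consent "must be recorded on the adverse event CRF (paper and/or electronic) whether or not related to study agent". Section 9.2.2 puts all operated patients in the safety analysis and then says: "Related AE and complications will be described".

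**Relatedness.** The grading sentence in 8.1 reads: "The possibility that the adverse event is related to study drug will be classified as one of the following", followed by five levels from not related to definite. The attribution item among the AE data elements refers to a study agent. The SAE report in Section 8 is to contain: "Description of the SAE, including attribution to drug and expectedness". The investigational product in Section 1.2 is the da Vinci SP system, and the treatment in Section 5.1 is an operation.

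**The concern.** The main concern is that the protocol gives two different answers to which serious events go to the IRB. Safety is a secondary objective, and Section 9.1 describes the system as pre-market. In a trial planned for 20 evaluable patients, one unreported serious event would matter. The protocol's own reporting rule should not leave out events that its own SAE definition includes.

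The secondary concern is the safety summary. Every AE is collected, but the stated commitment reaches AEs only through a causality judgement, and that judgement is worded for a drug trial. In a small single-arm feasibility study, a full account of AEs is more informative than one filtered by the investigator's view of cause.

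**Working it through.** No arithmetic applies. The protocol states no safety rate, and Section 9.1 says there is no formal testing or statistical calculation. The check sets the sections side by side.

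**1. Direction of the trigger.** In Section 8 the SAE is the cause and the malfunction is the result. A malfunction that harms a patient, which is the ordinary concern with a device, is the other way round and is not what the sentence says.

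**2. Width of the trigger.** Suppose the direction is corrected, so that the trigger is an SAE caused by malfunction. It is still narrower than 8.2, because none of the 8.2 criteria requires a malfunction.

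**3. Test cases, read literally.**

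| Event | SAE under 8.2? | Meets the Section 8 trigger? |
|---|---|---|
| Death, no malfunction | Yes | No |
| Bleed prolonging the hospital stay, no malfunction | Yes | No |
| Serious event linked to malfunction | Yes | Only if the event led to the malfunction |
| Unusual event meeting no seriousness criterion | No, but 8.2 says it is reported likewise | No |

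The last row shows that 8.2 assumes wider reporting. Extending the same reporting to events that miss the criteria makes sense only if events that meet them are already reported. The first two rows are not remote cases. Section 1.3 names "Perioperative risks related to the surgeries: bleeding, wound infection, adjacent organ injury, wound dehiscence", and any of these could become serious with the device working normally.

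**4. Section 8.3.** It routes SAE follow-up to the IRB with no malfunction condition. This is a difference in scope from Section 8. It does not state a separate rule for the initial report.

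**5. Recording against description.** Section 8.1 covers all AEs. Section 9.2.2 commits to related AEs and to complications. If the word related applies to AEs only, all complications are covered and the remaining AEs are covered only when judged related. If it applies to complications too, the commitment is narrower still. The first reading is used here because it is kinder to the plan.

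**6. Object of the judgement.** The protocol says study drug (8.1, grading), study agent (8.1, data elements) and drug (Section 8, report content). It defines no study drug or agent. Nearby wording points to carry-over from a drug template: 8.1 mentions a run-in and action taken with the agent, and 8.2 speaks of events at any dose.

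**7. What is untouched.** The complication, readmission, reoperation and mortality endpoints within 30 days (Section 2.2.2) do not pass through the relatedness wording of 9.2.2. Recording under 8.1 is complete.

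**The case against.** **On SAE reporting.** The strongest reply is that practice will be wider than Section 8. That section sends reports through the hospital's SAE procedures, and Sections 1.4 and 11 bind the trial to GCP and local regulation. This stands as far as it goes. A reader might infer that serious events will go unreported, but the documents do not show that, because the hospital procedures are not in hand. The contradiction inside the protocol remains, and a trigger that an outside procedure has to override should be corrected. A reader might also argue that Section 3.3 presupposes that the IRB hears of every life-threatening or fatal AE. That is only an inference, since 3.3 also lets the investigator terminate the trial. It is fair, too, that this part concerns reporting rather than statistics, and it is kept apart from the analysis point for that reason.

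**On 9.2.2.** The sentence is a minimum commitment. It does not say that other AEs will be left out, and detailed AE tables may sit in an SAP that is not shown. A reader who concludes that unrelated AEs will be dropped goes beyond the text. What stands is that the stated commitment is narrower than the data collected, for no stated reason.

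**On relatedness.** A reader might say that the judgement has no object at all. That is too strong. There is one product and one operation, and an investigator would readily read drug or agent as the SP procedure.

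Nor do other sections show that a separate procedure field is required. Section 4.3 withdraws patients with events "that do not have consequential correlations with the surgical procedures", but it gives its own examples and describes a withdrawal decision, not an item on the AE form. Section 1.3 sets surgical risks apart from conversion, which is a risk list and not a promise of two attributions.

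**Conclusion.** The main point holds on the text. The Section 8 trigger is reversed in direction and narrower than the SAE definition and reporting reach of 8.2, and the unseen hospital procedures do not remove that inconsistency. The secondary point holds as a matter of clarity and completeness: 9.2.2 commits to less than 8.1 collects, and the relatedness wording belongs to a drug trial.

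The size in events cannot be given. Counting the calendar visits after day 30, or the Section 1.3 risks that are not malfunctions, might look like a measure of effect. Such counts show only where the wording applies, and 8.1 requires all AEs to be recorded, not only those found at visits.

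The conclusion rests on a literal reading of Section 8 and on taking the word related in 9.2.2 to apply to AEs only. It does not assume that any event has been or would be missed. The text should be corrected, but the defect does not undermine the primary endpoint or the listed 30-day endpoints.

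**What to change.** 1. **Sections 8, 8.2 and 8.3:** reconcile them so that the IRB trigger covers SAEs as 8.2 defines them. List device malfunction as a separate reportable item.
2. **Section 9.2.2:** replace the sentence with: *All AEs and all complications in all operated patients will be described; the related subset will be shown separately.*
3. **Sections 8 and 8.1:** replace drug and agent, wherever causality is judged, with the SP device and/or the surgical procedure. Separate fields for the two are optional.

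The cost is wording, one more table and possibly a few more IRB reports. No extra AE collection is needed, because 8.1 already requires every AE to be recorded.
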